Data analysis will be performed in multiple stages. In the initial stage, preliminary analyses will be performed by examination of the distribution of variables to assess their characteristics (means, standard deviations, and skewness). Descriptive statistics and graphs will used to summarize the characteristics of the study population. Continuous measures will be tested for normality and homogeneity of variance. Non-normally distributed variables will be transformed to meet the normal distribution assumption for linear models. Randomization will be assessed by performing a series of Wilcoxon-rank sum tests, Chi-square or Fisher's exact tests to compare the groups on demographic and initial baseline clinical variables. Any variables on which the groups differ initially will be explored as covariates in subsequent analyses, and we will take this into account in the interpretation of the outcome. At the second stage, we will perform sensitivity analyses for the impact that potentially informative missing data may have on the analyses. We will use pattern-mixture models to assess if there is bias due to drop out or missing data. In addition, we will consider the extension of the pattern-mixture model, which allow subject-to-subject heterogeneity.

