At the final stage, hypotheses will be tested using Mixed Effects models, a generalized linear model described by Gibbons et al.⁹¹, Hedeker et al.⁹² and Laird et al.⁹³. Responses at baseline, throughout treatment (sessions 7, 13, 21), post treatment (session 26), 3- and 6-month follow-up will be nested within subjects. Intercept and slope will be modeled as random effects nested within subject; Treatment group, time, and group-by-time interaction will be a fixed effect. A fully saturated treatment by time model will be utilized for inference. Co-variance structure will be chosen based on Akaike's Information Criterion (AIC). Data will be analyzed from all randomized subjects on whom we have a baseline assessment and at least one post-baseline evaluation. If it is needed based on analyses on stage one, baseline covariates (e.g., demographics) will also be added to the model. All hypothesis tests will be intent-to-treat, and will be two-sided at the .05 level. We will adjust p-values for multiple testing within each hypothesis separately by using a Bonferroni correction whenever more than one variable is being tested. Although we didn't have any drop-out in out pilot study, we included a drop-out rate of 10% after the baseline assessment but prior to the first post-baseline evaluation in our power analyses.

Hypothesis 1.1-1.3: Relative to those assigned to ET alone, CREST participants will show significant reduction in **hoarding severity** (primary outcome), improvement in **functioning** (both functional capacity and self-reported functioning; secondary outcomes) and improvement in **quality of life** over time.

- Independent Variables: Treatment Groups (CREST and ET), Time points (baseline, throughout treatment (sessions 7, 13, 21), post-treatment (session 26), 3 and 6-month follow-up).
- Dependent Variable: Hoarding severity (SI-R), Functioning (UPSA, USORT, SLOF, WHODAS 2.0.), Quality of Life (Neuro-QOL).

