Power analyses are performed for all hypotheses, incorporating the longitudinal nature of the design. Within this design, repeated observations within subjects are potentially correlated. This has a profound impact on the resulting tests of significance⁹⁸. When the within subject correlation is properly incorporated, the repeated measures analysis takes full advantage of all information obtained from each subject, thereby greatly increasing statistical power over methods that compare treatments cross sectionally⁹⁹. Using the method described by Diggle, Liang, & Zeger¹⁰⁰ and Ahn et al.¹⁰¹, power calculations can be made for repeated measures designs under specified assumptions. Hedeker, Gibbons, & Waternaux¹⁰² extend Diggle et al.¹⁻³'s method for various covariance structures. Procedures describes by Hedeker et al.¹⁰² for Random Regression Models which incorporated these principles was used for the proposed study to estimated needed sample size (RMASS program provided by Hedeker for the Random Regression Model). The design assumptions consist of a 2 treatment groups and up to 7 visits (baseline, sessions 7, 13, 21, 26, and 3- and 6-month follow-up) where the slope is the dependent measure. Other assumptions used were alpha-level, nature of the hypothesis (two-sided versus one-sided), drop-out rate, and variance-covariance matrix of the longitudinal data. We assume a Type-I error level (alpha-level) of .01 to 0.05, drop-out rate of 15% and an autoregressive covariance structure. Data reported in the preliminary studies section which included our own pilot studies were used to calculate effect sizes. From the preliminary analysis of pilot study, the estimated standard deviation (SD) for SI-R score ranges from 12.75-12.82 and the between visit correlation coefficient of 0.71. We considered a range of estimates of stand deviations of 12.5, 12.8 and 13.0, and correlations of .45 to 0.70 in our power analysis. We have reported large effect sizes of 1.02 and 1.51 from our previous studies which converted to differences of 60 to 37 for our primary outcome. However, for these calculations, we conservatively selected smallest clinically meaningful differences that we would like to be able to detect. This was then converted to a medium effect size, defined mathematically as a between-group difference increasing linearly from 0 at baseline to .5 SD units at the last time point. Calculations using the above assumptions indicated that the study will have minimum power of 80% to yield a statistically significant result for a medium effect size with the proposed sample size of 136 patients (68 for each of the two groups).

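### The pattern-mixture check on drop-out is unspecified and, at the planned drop-out, a null result could not rule out bias large enough to change the SI-R conclusion

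*Combined protocol and SAP*

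**What the plan says.** In the Statistical Plan of the combined protocol and SAP, the second stage consists of sensitivity analyses for potentially informative missing data. The method is given in one sentence, "We will use pattern-mixture models to assess if there is bias due to drop out or missing data", followed by "we will consider the extension of the pattern-mixture model, which allow subject-to-subject heterogeneity". No drop-out patterns, identifying restriction, size of departure or decision rule is stated.

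The final, hypothesis-testing stage is restricted to "all randomized subjects on whom we have a baseline assessment and at least one post-baseline evaluation", and the tests are described as intent-to-treat. On power, the same paragraph says "we included a drop-out rate of 10% after the baseline assessment but prior to the first post-baseline evaluation". The Power Analysis section instead assumes a "drop-out rate of 15% and an autoregressive covariance structure". How the two rates relate is not stated.

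The opening paragraph of the Statistical Plan adds tests of whether drop-out is completely random and a baseline comparison of drop-outs with completers.

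**The concern.** A pattern-mixture model estimated from the data learns how drop-outs differ from completers only through drop-outs who have follow-up measurements. A patient who leaves before the first post-baseline visit has no slope and falls outside the final-stage analysis set. At the planned rates few drop-outs are left to inform the model, possibly none. What happens after they leave is not observed at all, so it has to come from an assumption, and the plan states none.

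Informative loss is foreseeable here. The description of CREST credits the cognitive training with giving patients the skills to comply, attendance included, and Hypothesis 2.1 makes adherence a mediator of SI-R reduction. Drop-out could therefore depend on both arm and outcome. The risk is that a null result from the planned model is taken as evidence of no bias when it could not have excluded a bias that matters.

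**Working it through.** **Inputs.** From Power Analysis: 136 patients (68 per arm), 7 visits, SI-R SD about 12.8, between-visit correlation r from .45 to .70, drop-out 15%, 80% power, and a target difference rising linearly from 0 at baseline to 0.5 SD at the last visit. From Statistical Plan: two-sided alpha .05, and 10% drop-out before the first post-baseline visit.

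**1. The plan's own figure.** Take seven equally spaced visits, autoregressive correlation .70 and no baseline difference. The variance factor is v = 36/(t'R⁻¹t) with t = 0,…,6.
- t'R⁻¹t = 19.95/0.51 = 39.12, so v = 0.920.
- n per arm = 2 × 0.920 × 2.80²/0.5² = 57.8, and 57.8/0.85 = 68. The stated 136 is reproduced with 15% loss.
- The design SE is √(2 × 0.920/57.8) = 0.178 SD. At r = .45 it is 0.159 SD.

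**2. Drop-outs with post-baseline data.** 10% of 136 is 13.6 and 15% is 20.4.

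| Reading of the two rates | Early, baseline only | Later, with follow-up |
|---|---|---|
| 10% only, all early | 13.6 | 0 |
| 15% in total, of which 10% early | 13.6 | 6.8 |
| 15%, all later | 0 | 20.4 |
| 10% early plus 15% later | 13.6 | 20.4 |

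**3. What the model could detect.** The quantity is the arm difference in (drop-out minus completer) SI-R change. In SD units,

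SE = √[2(1−r)] × √[2(1/n_d + 1/n_c)],

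where n_d and n_c are drop-outs and completers per arm. The detectable difference is 2.80 × SE. Here n_c = 68 × 0.85 = 57.8.

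| Informative drop-outs | r | SE (SD) | Detectable, 80% power | Power at 1 SD | Power at 0.5 SD |
|---|---|---|---|---|---|
| 7 (n_d = 3.4) | .70 | 0.611 | 1.71 SD (22 points) | 37% | 13% |
| 7 (n_d = 3.4) | .45 | 0.828 | 2.32 SD (30 points) | 23% | 9% |
| 20 (n_d = 10) | .70 | 0.375 | 1.05 SD (13 points) | 76% | 27% |
| 20 (n_d = 10) | .45 | 0.508 | 1.42 SD (18 points) | 50% | 17% |
| 0 | any | – | not estimable | – | – |

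In the last reading of step 2, n_c falls to 51 per arm, which leaves the rows for 20 almost unchanged (1.05-1.43 SD). These figures are lenient, because they give drop-outs a change score as precise as that of completers. On slopes extrapolated to the last visit, 7 drop-outs give 2.3-2.5 SD if each has five post-baseline visits and 9.2-11.5 SD if each has only one.

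**4. What size of departure matters.** Suppose 15% of CREST patients are missing and are 1 SD worse than the model assumes, while ET drop-outs are as assumed. The arm effect shifts by 0.15 × 1 = 0.15 SD, and 0.15/0.5 = 30% of target. With 10% missing the shift is 0.10 SD, or 20%.

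The significance boundary is 1.96 × 0.178 = 0.35 SD. An observed 0.5 SD reaches it after a shift of 0.15 SD, so the tipping shift is 0.15/0.15 = 1.0 SD, about 13 SI-R points. With the r = .45 SE the boundary is 0.31 SD and the tipping shift is (0.5 − 0.31)/0.15, about 1.25 SD.

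**The case against.** Several stronger readings are tempting, and the documents do not support them.

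- **That the analysis set excludes most drop-outs.** This needs the 10% to be nested in the 15%, and the final-stage set to apply to stage two as well. Neither is stated, and the excluded share runs from 0% to 100% across the readings. Exclusion is not the main cause either. Patients with only a baseline carry no slope information even if kept, and with 20 late drop-outs and none excluded the detectable difference is still at least twice the 0.5 SD target.
- **That a real departure would almost always go unseen.** Power at 1 SD is 23-37% with 7 informative drop-outs and 50-76% with 20, which is low to moderate.
- **That only implausibly large bias is detectable.** This confuses a pattern difference with bias in the overall effect. A pattern difference of 1.7-2.3 SD, weighted by 3.4/61.2 = 5.6%, moves the overall effect by 0.10-0.13 SD. Weighted by 15% it moves it by 0.26-0.35 SD. Either bias is material, but neither is implausible.
- **That the check is bound to look reassuring.** The plan sets no significance-test rule and describes the stage as gauging the impact of missing data. A pattern-averaged estimate could serve that purpose. With 7 informative drop-outs its SE in a slope model is 1.00-1.42 times the pooled SE, so a wider interval might itself give warning.

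The plan is also not silent elsewhere. Its baseline comparison can include early leavers, and the group reports low past attrition (Retention section). If attrition is lower than planned, the possible bias shrinks as well. But the baseline comparison says nothing about outcomes after drop-out, and a test for completely random drop-out neither imputes values nor addresses loss that depends on unseen outcomes. What stands is under-specification, together with the weak evidence a null result would give.

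**Conclusion.** The concern holds as a limit on what the planned analysis can show. On every reading of the two drop-out rates, a null pattern-mixture result would be weak evidence against a drop-out effect of about 1 SD. In the planning model a CREST-only departure of that size takes an observed 0.5 SD to the significance boundary. No stated analysis of SI-R covers all 136 randomised patients.

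The result assumes equal drop-out in the two arms, SD 12.8, r from .45 to .70, a baseline-to-last-visit correlation equal to r, and change-score precision for drop-outs. Under autoregressive decay the detectable differences would be larger. The tipping figure assumes 15% missing, an observed effect of exactly 0.5 SD and the design SE held fixed. A larger SE brings the boundary nearer, and a larger observed effect moves it away. The step from a pattern difference to a departure from the model's assumption is approximate, because the mixed model already uses what late drop-outs contributed.

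This does not show that the trial's result will be biased, or that pattern-mixture modelling is the wrong family of method. The planned version has no stated anchor for the part the data cannot supply.

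**What to change.** Specify the stage-two sensitivity analysis of SI-R as a delta-adjusted (tipping-point) multiple imputation covering all 136 randomised patients, including those with only a baseline. This is itself a pattern-mixture model, with the unidentified part set by a stated delta. Shift the imputed post-drop-out values by arm over a pre-stated grid, for example 0 to 1 SD with CREST worse than ET, and report the shift at which the conclusion changes. Since the tipping shift is about 1.0 SD at r = .70 and 1.25 SD at r = .45, a grid reaching somewhat beyond 1 SD would be safer.

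Keep any model that estimates pattern effects from the data as supportive only. Define its patterns and identifying restriction, and state that a null pattern effect will not be read as absence of bias. Reconcile the 10% and 15% rates, saying whether one includes the other and which was used for the sample size; 15% alone reproduces 68 per arm.

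The cost is SAP wording and slightly more programming. The downside is that the report gives a range of results instead of one test. Neither the sample size nor the visit schedule changes.

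### The primary model gives each arm its own baseline SI-R mean and names no primary contrast, so the 80% power claimed for a slope with zero baseline difference is not shown for the planned analysis

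*Combined protocol and SAP*

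**What the plan says.** **Statistical Plan, final stage.** Baseline, sessions 7, 13 and 21, session 26 and the two follow-ups are all responses nested within subject. For the mean: "Treatment group, time, and group-by-time interaction will be a fixed effect" and "A fully saturated treatment by time model will be utilized for inference". For the covariance: "Intercept and slope will be modeled as random effects nested within subject", with the structure to be picked by AIC. Nothing sets the arms equal at baseline. Hypotheses 1.1-1.3 refer to change over time without naming a visit, a contrast or a joint test.

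**Power Analysis.** The design has up to seven visits, "where the slope is the dependent measure". The effect is "a between-group difference increasing linearly from 0 at baseline to .5 SD units at the last time point". The assumptions are a "drop-out rate of 15% and an autoregressive covariance structure", alpha from .01 to .05, and "correlations of .45 to 0.70 in our power analysis"; the pilot correlation was .71. The claim is "minimum power of 80% to yield a statistically significant result for a medium effect size with the proposed sample size of 136 patients".

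**Recruitment and Randomization.** The baseline assessment decides eligibility and so comes before the 1:1 allocation.

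**The concern.** A saturated model for two arms and seven visits has 14 free means, two of them at baseline. Randomisation makes the true baseline means equal, so estimating them separately removes no bias and spends precision. With complete data, a change contrast at a visit from this model is simply the unadjusted difference in mean change.

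The Power Analysis describes something else: one slope, with no difference at baseline. The saturated model can yield a visit contrast, a linear contrast or a 6-df interaction test, and the plan does not say which one decides the trial. If the stated 80% belongs to a more efficient analysis than the one that will be run, the trial could be much weaker than it claims. Leaving the test unnamed also leaves a choice among several primary results.

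**Working it through.** **Inputs.** SD 1; difference rising linearly from 0 to 0.5 at the last visit; two-sided alpha .05; AR(1) with r from .45 to .70; 15% drop-out counted as wholly lost, so 68 x .85 = 57.8 per arm (all from the Power Analysis). Equal spacing, t = 0, 1/6, ..., 1, is my assumption. S is the 7 x 7 correlation matrix.

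**1. Reproducing 136.** For a slope with zero baseline difference, the per-patient variance is v = 1/(t'S⁻¹t). For AR(1), t'S⁻¹t = Σ(t_k - r·t_(k-1))²/(1 - r²). At r = .70 the numerators are (1.0² + 1.3² + 1.6² + 1.9² + 2.2² + 2.5²)/36 = 19.95/36 = .5542. Dividing by .51 gives 1.0866, so v = .9203. Then n per arm = 2 x .9203 x (1.960 + .842)²/.25 = 57.8, and 57.8/.85 = 68, a total of 136.

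**2. Same slope, separate baselines.** Now v is the slope element of (X'S⁻¹X)⁻¹ with X = [1, t]. At r = .70, 1'S⁻¹1 = 2.0588 and 1'S⁻¹t = 1.0294. The information is 1.0866 - 1.0294²/2.0588 = .5719, so v = 1.7486. Total N becomes 136 x 1.7486/.9203 = 258. Power with 57.8 per arm is Φ(.5/√(2 x 1.7486/57.8) - 1.96) = Φ(.073) = 53%.

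**3. Saving for one visit contrast.** Variance is 2(1-r) with separate baselines and 1-r² with a shared one, where r is the baseline-to-visit correlation. The saving is (1-r)/2.
- Constant correlation: (1-.71)/2 = 14.5%; (1-.45)/2 = 27.5%.
- AR(1), r .70 to .45: session 7, 15-27.5%; session 26, (1-.70⁴)/2 = 38% to (1-.45⁴)/2 = 48%; 6 months, (1-.70⁶)/2 = 44% to (1-.45⁶)/2 = 50%.
- Random intercept and slope: the documents give no slope variance, so the saving is unknown. If the slope SD is 0.25-1.0 baseline SD per year, the intercept share .45-.70 and the intercept-slope correlation -.3 to .3 (all assumed), it runs from about 0 to 31% at weeks 26 and 52.

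**4. Power under the planning AR(1)** (r .45-.70, 57.8 per arm, alpha .05):

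| Test | Separate baselines | Shared baseline |
|---|---|---|
| Linear-trend slope | 50-53% | 80-88% |
| 6-month contrast | 48-53% | 77% |
| Linear contrast in the saturated model | 47-49% | 68-69% |
| 6-df interaction | 26-28% | 52-64% |

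The linear contrast uses weights proportional to t minus its mean. The 6-df test uses the noncentral chi-square. At alpha .01 the shared-baseline slope has 59-71%.

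**5. Power at constant correlation.** At r = .71 all these tests exceed 91% with either model. At r = .45 the 6-month contrast goes from 73% (separate) to 85% (shared). The 6-df test goes from 66% to 80% with equal spacing, or 63% to 75% on actual weeks. The saturated linear contrast is already at 88-89%.

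**6. A contrast inside the saturated model.** Let V be the covariance of the six post-baseline visits given baseline, and d the assumed linear effect at those visits. The post-baseline block of S⁻¹ equals V⁻¹ and t is 0 at baseline, so d'V⁻¹d = .25·t'S⁻¹t. A contrast with prespecified weights V⁻¹d therefore has exactly the slope's power, 80-88%. Simple averages also help: at r = .45 the mean of the last two visits has 82.5% and of the last three 83.8%. At r = .70 the mean of the last two has variance (.9717 + .9862 + 2 x .6802)/4 = .8296 and effect .4583, hence Φ(.4583/√(2 x .8296/57.8) - 1.96) = 77%.

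**The case against.** Separate baseline means are a standard and valid choice. In simulation with 58 per arm and 40,000 runs, type I error was .049-.053 with either model. A reader might infer bias or a false-positive problem; there is none.

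A reader might also infer that the trial as it will be analysed has about 50% power. The documents do not support that. Pure AR(1) is a planning assumption; the analysis uses random intercepts and slopes with covariance chosen by AIC. In one assumed random-slope case the simulated power of the saturated linear contrast was .827 with separate and .824 with shared baselines: no gain and no shortfall. This limits the size of the point, but the sponsor's own planning covariance still does not deliver the sponsor's own figure.

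Nor does the match to 136 show which model was used for sizing. A zero difference at baseline is an assumed effect shape that any randomised trial would adopt. Other routes land close: the shared-baseline 6-df test at constant r = .45 gives 135.9, and a two-sample comparison at the last visit with 10% drop-out gives 140, though neither is the slope under AR(1) that the section describes. The match also depends on spacing: with t in actual weeks at r = .70, power is 78%, or 79.9% if the correlation lags are also in weeks.

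Finally, the plan allows covariates for imbalanced baseline variables, but only if they pass two p-value screens, which does not guarantee use of baseline SI-R. Counting 15% as wholly lost is somewhat harsh, since the model keeps partial data. With the 10% in the Statistical Plan (61.2 per arm), the separate-baseline slope still has only about 53-55% at r .60-.70.

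**Conclusion.** The point holds as a loss of precision and a mismatch between the sized and the specified analysis. Under the Power Analysis's AR(1), 15% drop-out and alpha .05 with equal spacing, none of the four separate-baseline tests checked exceeds 53%, against a stated minimum of 80%. The shared-baseline slope meets 80% at alpha .05 but not at the .01 end of the stated range. Under constant correlation the effect is modest at r = .45 and of little consequence at .71; under random slopes it cannot be sized from the documents and may be nil. The missing primary contrast is a gap under every covariance.

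It would go too far to conclude that the saturated model must give way to a linear-trend slope. Step 6 shows that a prespecified weighted contrast in the saturated model with a shared baseline has the same power. Linearity there only sets the weights; the test stays valid if the true effect is not linear.

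**What to change.** 1. In the Statistical Plan, constrain the baseline mean to be equal across arms: fixed effects for time and for treatment by post-baseline time, with no treatment term at baseline. The saturated post-baseline means can stay.
2. Name one primary test for SI-R: a visit contrast, a prespecified average or weighted contrast of post-baseline visits, the slope, or the 6-df interaction. If it is weighted, fix the weights in advance.
3. In the Power Analysis, restate power for that test, in that model, with the covariance and a single alpha given. Sharing the baseline does not by itself bring the 6-month contrast, the saturated linear contrast or the 6-df test to 80% under AR(1). If one of these is chosen, state the lower power or justify another covariance.

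The cost is SAP wording and a recalculation, with no new data or patients. The constraint is valid because baseline precedes randomisation. It should be written down before outcomes are compared by arm; if that has already happened, report the constrained model as a sensitivity analysis.

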- Statistical Analysis: The dependent variable will be analyzed by mixed effects model methods as described above. Baseline demographic and other clinically important characteristics at baseline will be assessed for imbalance between the two groups and their association with the outcome using a univariate analysis. Those found to be significantly unbalanced between intervention groups (p < 0.10) and moderately associated with the outcome (p < 0.15) will be included as covariates in the model. We will adjust p-values for multiple testing within each hypothesis separately by using a Bonferroni correction whenever more than one variable is being tested

Hypotheses 2.1: Treatment adherence, improvement in executive functioning, and reduction in avoidance will mediate hoarding symptom reduction in CREST.

Dependent Variables: Hoarding severity (SI-R)

Independent Variables: Executive Functioning (D-KEFS scaled scores and PCET), Avoidance (AAQ and BAT) and Treatment Adherence score.

Statistical Analysis: The effect of mediator variables will be tested following the procedures recommended by Kraemer⁹⁴, Bauman⁹⁵, Cohen and Cohen⁹⁶, and Busemeyer and Jones⁹⁷. Briefly, treatment mediators explain how or why one variable affects the treatment effect and are defined as mechanisms through which a treatment might achieve its effects. The mediator's effect is measured during the treatment and is correlated with treatment choice and may possibly be a result of treatment and have either a main or interactive effect on the outcome. The dependent or outcome measure (SI-R) will be evaluated throughout the study and will be used as a repeated measure for all the available time points. In essence, the slope of each outcome measure on time will be used as a dependent measure. The mediator and bootstrap technique will be used to calculate a 95% confidence interval for mediation effect. Random effects models will be used for analysis and the change score of mediators will be included in the model.

Hypotheses 2.2: Symptom severity reduction and improved functional capacity will mediate improved quality of life in CREST.

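### No SI-R contrast, time coding or baseline rule is named for Hypothesis 1.1, so the stated 80% power belongs to a slope test that the Statistical Plan does not specify

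*Combined protocol and SAP*

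**What the plan says.** The final stage of the Statistical Plan fits a mixed model to SI-R at baseline, sessions 7, 13 and 21, after session 26, and at 3 and 6 months. Its structure is given as "Intercept and slope will be modeled as random effects nested within subject" and "Treatment group, time, and group-by-time interaction will be a fixed effect", followed by "A fully saturated treatment by time model will be utilized for inference". The covariance structure is left to AIC. Tests are two-sided at .05.

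Hypothesis 1.1–1.3 claims a greater reduction with CREST than with ET over time. Its analysis paragraph adds only "The dependent variable will be analyzed by mixed effects model methods as described above". No section names a visit, a contrast or degrees of freedom for SI-R, says whether time is categorical or continuous, or says how a baseline group difference is handled.

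The Power Analysis is specific. It takes seven visits "where the slope is the dependent measure", an effect defined as "a between-group difference increasing linearly from 0 at baseline to .5 SD units at the last time point", and a "drop-out rate of 15% and an autoregressive covariance structure". It states at least 80% power with 136 patients, 68 per arm.

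**The concern.** If the saturated model means free group means at every visit, it has no single slope parameter. Its usual overall test of group by time has 6 df, and that is not the test that was powered. A joint test also carries no direction, so superiority of CREST would have to be read from visit estimates for which the plan gives no decision rule.

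A second gap matters about as much. Baseline is a response and group is a free fixed effect, so as written the model estimates a baseline difference. The power calculation starts that difference at zero.

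Two things are at stake: whether the 80% applies to the test that will be run, and whether the primary test could be chosen after the data are seen. The Bonferroni rule applies when several variables are tested. It does not cover a choice among visits or contrasts of the one variable SI-R.

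**Working it through.** **Inputs from the Power Analysis.** Seven visits; difference 0 at baseline rising linearly to 0.5 SD; correlation .45 to .70; autoregressive covariance; 15% loss; 68 per arm. Two-sided .05 is from the Statistical Plan.

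**Assumptions added here.** First-order autoregression per visit step, AR(1); all loss before the first post-baseline visit, so n = 68 × 0.85 = 57.8 per arm; normal and chi-square approximations. Visits are first taken as equally spaced. The difference is then made linear in assumed weeks 0, 7, 13, 21, 26, 39 and 52, with the correlation still per visit step.

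**Step 1: reproduce the 80%.** With unit SD, d_k = 0.5 × k/6 for k = 0 to 6. With the baseline difference fixed at 0, the trend estimated with model-based (GLS) weights has noncentrality λ = d′[(2/n)R]⁻¹d. Because d_0 = 0, under AR(1) this is

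λ = (n/2) × Σ(d_k − r·d_{k−1})² / (1 − r²), summed over k = 1 to 6.

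- r = .70: 28.9 × 0.13854/0.51 = 7.85, giving 80.0% power on 1 df.
- r = .45: 28.9 × 0.27179/0.7975 = 9.85, giving 88.1%.

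In weeks, λ is 7.47 and 8.65, giving 78.1% and 83.7%. The plan's figure is therefore a 1-df trend with no baseline difference.

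**Step 2: same inputs, 6-df joint test.** The assumed difference is exactly linear, so λ is unchanged and only the df differ. Equally spaced, power is 52.2% (r = .70) and 63.6% (r = .45). In weeks it is 49.8% and 56.9%. Reaching 80% needs λ = 7.849 on 1 df but 13.624 on 6 df, a ratio of 1.736. At r = .70, equally spaced, that is 136 × 1.736 ≈ 236 enrolled.

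**Step 3: leave the baseline difference free.** With W = [(2/n)R]⁻¹ and slope b = 0.5/t_last, λ = b² × [t′Wt − (1′Wt)²/(1′W1)]. Under AR(1) this is 3.93 to 4.32, giving 51–55% for the trend and 27–29% for the joint test.

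**Step 4: vary the covariance.** Power at n = 57.8, over both correlations and both time scales:

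| Covariance | Baseline difference | 1-df trend | 6-df joint |
|---|---|---|---|
| AR(1) | fixed at 0 | 78–88% | 50–64% |
| AR(1) | free | 51–55% | 27–29% |
| Compound symmetry | fixed at 0 | 94–99.6% | 75–95% |
| Compound symmetry | free | 88–99% | 63–92% |

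**Step 5: single visits.** Under AR(1) the baseline-adjusted difference at visit k has variance (1 − r²ᵏ) × 2/n, because its correlation with baseline is r to the power k. At 6 months (0.5 SD) power is 77% at either correlation. After session 26 it is 43–46% equally spaced and 27–28% in weeks.

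**Step 6: loss rate.** The Statistical Plan gives 10% loss rather than 15%. Then n = 61.2, and with equal spacing, AR(1) and baseline fixed, the trend has 82–90% and the joint test 55–67%.

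**The case against.** The best reply is that the sections agree and the wording is merely loose. The Power Analysis says it covers all hypotheses, so its slope includes Hypothesis 1. A random slope needs time as a number. Under Hypothesis 2.1 the plan writes "In essence, the slope of each outcome measure on time will be used as a dependent measure". The saturation sentence comes directly after the list of group, time and their interaction, and may mean only that all three terms are kept with linear time.

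That reading is possible, and it is why the text is called ambiguous rather than contradictory. It does not close the gap. A random slope describes variation between subjects and does not name the fixed effect to be tested. The slope sentence belongs to the mediation analysis. With linear time and a free group effect, the trend still has only 51–55% under AR(1), so the baseline rule remains decisive.

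A reader might infer that the plan commits to a 6-df test and so has about half the power it claims. The documents do not support this, because no such test is written. Nor do they show that 51–55% is the trial's power. The covariance is to be chosen by AIC, and under compound symmetry the trend keeps about 88% or more under either baseline rule. The Statistical Plan also specifies a random intercept and slope, but no variance components are given, so power under that structure cannot be computed from the documents.

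**Conclusion.** The point holds as a gap in specification with a material consequence. The 80% is correct for a 1-df trend with no baseline difference, but the Statistical Plan specifies neither that trend nor that constraint for Hypothesis 1.1. Under the plan's own autoregressive structure and 15% loss, the readings its wording permits for the overall group-by-time comparison run from 27% to 88% power.

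That the contrast, time coding and baseline rule are missing is plain from the text. The size of the loss is less certain. It rests on AR(1), early loss and an exactly linear difference, and it is smaller under compound symmetry. Even there the joint test can fall below 80%: to 75% with baseline fixed and 63% with baseline free, both at r = .45 with the difference linear in weeks.

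**What to change.** In the Statistical Plan, replace the saturation sentence with one that names a single 1-df primary contrast for SI-R. Leave visit means unstructured after baseline, and either constrain the baseline means to be equal or use baseline as a covariate. A model with baseline constrained is no longer fully saturated, so the wording has to change. State the time scale (visit or week) and the weights.

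The contrast that matches the Power Analysis is the linear trend in the CREST-minus-ET difference over the seven visits, with 78–88% power under AR(1), 15% loss and model-based weights. Weights matter: fixed weights 1 to 6 on the baseline-adjusted visit differences give 74–86% (equal spacing). The baseline-adjusted difference at 6 months is an acceptable alternative if the power is restated to 77% at 15% loss. The sponsor may prefer another contrast, provided the power line is recalculated for it. Report the joint interaction and the other visits as supportive, and use one loss rate in both sections.

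The cost is a sentence or two and a matching power line, with no added patients or visits. The downside is that the primary claim is tied to one contrast, and a linear trend loses power if the true difference is not linear. As an illustration, assume a difference of 0 through session 26, then 0.25 and 0.5 SD (AR(1), n = 57.8, equal spacing). The trend then has 58–63% and the 6-month difference 77%.
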